7.2.2 Grading severity

Adverse events will be assessed according to the Common Toxicity Criteria for Adverse Events [CTCAE] version 4.03. If CTCAE grading does not exist for an adverse event, the severity of mild, moderate, severe, and life-threatening, **or** Grades 1 - 4, will be used. CTCAE Grade 5 (death) will not be used in this study; rather, this information will be collected in the End of Treatment or Survival Information CRF page. Adverse event monitoring should be continued for at least 4 weeks following the last dose of study treatment.

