7.2 Recording and Grading of Adverse Events

7.2.1 Recording

All observed or volunteered adverse events, regardless of treatment group, severity, suspected causal relationship, expectedness, or seriousness will be recorded on the Medical History/Current Medical Conditions Electronic Case Report Form.

The occurrence of adverse events should be sought by non-directive questioning of the patient at each visit during the study. Adverse events also may be detected when they are volunteered by the patient during or between visits or through physical examination, laboratory test, or other assessments. As far as possible, each adverse event should be evaluated to determine:

- a. The severity grade (CTCAE grade 1-4)
- b. Its relationship to each study drug (suspected/not suspected)
- c. Its duration (start and end dates or if continuing at final exam)
- d. Action taken (no action taken; study drug dosage adjusted/temporarily interrupted; study drug permanently discontinued due to this adverse event; concomitant medication taken; non-drug therapy given; hospitalization/prolonged hospitalization)

Adverse events (but not serious adverse events) occurring before starting study treatment, but after signing the informed consent form are recorded on the Medical History/Current Medical Conditions Electronic Case Report Form. Abnormal laboratory values or test results constitute adverse events only if they induce clinical signs or symptoms, are considered clinically significant or require therapy (e.g., any hematologic abnormality that requires

transfusion or cytokine treatment), and should be recorded on the Adverse Events CRF under the signs, symptoms or diagnosis associated with them. In addition, isolated abnormal laboratory values that are considered clinically significant (e.g., cause study discontinuation or constitutes in and of itself a Serious Adverse Event) should be recorded on the Adverse Events CRF. SAEs occurring after the start of treatment are recorded on the Adverse Event CRF.

A clinically significant change in a physical examination finding or an abnormal test result should be recorded as an AE, if it:

- is associated with accompanying symptoms,
- requires additional diagnostic testing or medical or surgical intervention,
- leads to a change in study dosing or discontinuation from the study,
- requires additional concomitant drug treatment or other therapy, or
- is considered clinically significant by the investigator.

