7.4 Serious Adverse Event Reporting

Within 24 hours of awareness of a serious adverse event, whether or not related to the study drug, the investigator will complete and submit a Medwatch 3500a form, containing all required information (reference CFR § 312.32). The investigator will submit a copy of this Medwatch 3500a form to the sponsor-investigator and Esanik by either e-mail or fax, within the same timeframe.

The SAE documentation, including the Medwatch 3500A form and available source records should be emailed or faxed to:

Email: [contact]

[contact]

The following minimum information is required:

- study number
- subject number, sex and age
- the date of report
- a description of the SAE (event, seriousness of the event)
- causal relationship to the study drug. Follow-up information for the event should be sent within 7 days as necessary. Copy of above should also be sent to coordinating site (PI- [name]).

Sponsor-Investigator:

[name] FACP
[name]
[name]

[contact]
[contact]
Email: [contact]

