8.3.5 Evaluating best overall response

The best overall response is the best response recorded from the start of treatment until either disease progression or recurrence. The investigator's determination of best overall response will be based both on response criteria and on confirmation criteria (Table 9). To be assigned a status of partial response or complete response, changes in tumor measurements must be confirmed by repeat assessment performed 4-6 weeks after the criteria for response are first met. To confirm stable disease, follow-up measurements must meet SD criteria at a minimum interval of 6-8 weeks after SD was first documented.

Note: If unconfirmed progression noted at the first time point is not confirmed at a second time point, the next assessment time point after the first that meets the criteria for progression will be treated as time point 1.

Table 9. Assessing Overall Response.

Target Lesions	Nontarget Lesions	New Lesions	Overall Response
CR	CR	No	CR
CR	Incomplete response/SD	No	PR
PR	Non-PD	No	PR
SD	Non-PD	No	SD
PD	Any	Yes or No	PD
Any	PD	Yes or No	PD
Any	Any	Yes	PD

Abbreviations: CR, complete response; PD, progressive disease; PR, partial response; SD, stable disease.

Subjects with global deterioration of health status who require treatment to be discontinued without objective evidence of disease progression should be classified as having symptomatic deterioration. Every effort should be made to document their objective progression, even after discontinuing treatment.

Subjects who do not have tumor response assessment due to rapid progression or toxicity will be considered nonresponders, will be included in the denominator for the response rate, and will be classified into one of the categories listed below:

- death attributed to disease progression
- early discontinuation attributed to disease progression
- death attributed to drug toxicity
- early discontinuation attributed to drug toxicity

Note: If a subject receives subsequent therapy before tumor progression is documented, the reason for changing therapy must be reported. Reasons include clinical progression, drug toxicity, or secondary therapy for maintaining tumor response.

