11.2 Endpoints

11.2.1 The first primary endpoint (PSA50) is a PSA decline of $\geq 50\%$ from baseline (PSA50), using the PCWG3 criteria. Refer to Section 8.2.1.

The second primary endpoint(s) (toxicities) is (are) defined in Section 7. Adverse events of all grades will be captured by the National Cancer Institute - Common Terminology Criteria for Adverse Events, version 4.03 (NCI-CTCAE v4.03) and GCP standards.

11.2.2 The secondary endpoints are defined as follows:

Time to PSA response (TTPR) is defined as the time from treatment start until the first documented occurrence of PSA50. PSA50 is defined in Section 1.3.

Duration of PSA response (PRD) is defined as the time from start of PSA50 until PSA progression (defined in Section 8.3.2).

PSA progression free survival (PPFS) is defined in Section 8.3.2 except that it will be based on PSA assessments only. PSA progression rates will be estimated from the PSA-only PFS distribution.

11.2.3 The correlative/exploratory/tertiary endpoints (and the methods of their determination) are described in Section 9.

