11.4 Analysis

11.4.1 For the Primary Objectives, all analyses point and (1-sided Wilson type 90% lower) CI estimates of the primary endpoint (PSA50) will be calculated.

Adverse events will be tabulated by incidence and severity graded according to the National Cancer Institute – Common Terminology Criteria for Adverse Events (CTCAE) version 4.03. Other statistics will include point and (2-sided) CI estimates of overall toxicity and of specific types of toxicity.

11.4.2 For Secondary Objective 1, descriptive statistics of TTPR will be used to summarize the time to PSA response. These descriptives will include N, median, mean, standard deviation (SD), interquartile range (IQR), minimum, and maximum.

11.4.3 For Secondary Objectives 2 and 3, the censored distributions of duration of response (RD) and PSA progression free survival (PFS) will be summarized with the Kaplan-Meier (K-M) survivorship estimate. A graph of the K-M curve for PRD and for PPFS will be generated along with the Hall-Wellner 90% confidence band, and a display of the number of patients at risk at several time points, below the X-axis. Summary statistics (6-month rate, 12-month rate, median, etc.) will be calculated from the K-M life table, each one with its respective 80% confidence interval (CI).

11.4.4 For the Correlative (Exploratory) Objectives, frequency distributions of all categorical variables (grade of specific types of toxicity, and categorical biomarkers or other correlatives) will be generated. Serial PSA levels will be displayed using spaghetti plots, and changes in PSA using waterfall plots.

Descriptive statistics will be used to summarize all continuous correlatives (e.g., PSA, continuous biomarkers and other correlatives), and changes in them pre/post ESK981 treatment. Gene expression levels will be \log_2 transformed prior to descriptive analysis. Multiple boxplots and scatterplots will be used to display summary statistics of biomarkers/correlatives and interrelationships between continuous correlatives, respectively.

Details of the planned determination of bioinformatics correlatives are given in Section 9. Response (whether PSA50 or overall), a categorical clinical outcome, will be statistically modeled as a function of each correlative using exact logistic regression. TTPR, a continuous

uncensored clinical outcome (limited to only the PSA50 responders), will be statistically modeled as a function of each correlative using linear regression.

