APPENDIX F. DSM REPORT FORM

PROTOCOL#:

REPORT DATE:

PROTOCOL TITLE					
PROTOCOL ACTIVITY SINCE LAST REPORT					
Accrual Goal:		Eligible:			Total number of AE's to date:
Accrual to Date:		Ineligible: (provide reason):			
Accrual Since					
Last Monthly Report:					
SPECIFICALLY FOR PHASE I TRIAL &/OR DOSE ESCALATING TRIALS:					
DOSE LEVEL	ACCRUAL				
RECORD ALL GRADE 3, 4, AND 5 ADVERSE EVENTS (AE). GROUP BY CATEGORY OF AE. RECORD THE DATE OF THE OCCURRENCE, ATTRIBUTION AND IF REPORTABLE TO THE IRB. SHADE THE ROWS OF THE AE'S THAT HAVE OCCURRED FOR THIS REPORT. ATTACH THE HIC UP REPORT FORM FOR THESE REPORTABLE EVENTS THAT OCCURRED ON THIS REPORT.					
Pt. ID#	Category and type of adverse reaction		Date of Occurrence	Grade ¹	Attribution ²

1. Grade: 1-Mild, 2-Moderate, 3- Severe, 4-Life-threatening, or 5- Death. 2. Attribution: 1-unrelated, 2 - unlikely, 3 - possibly, 4 - probably, or 5 - definitely
					
OFF TREATMENT  Provide reason [progression, death, toxicity, completed therapy, etc].					
PROTOCOL VIOLATIONS  Deviations from protocol treatment, monitoring, or study calendar.					
PROTOCOL AMENDMENTS  Include date submitted to regulatory bodies and date approved.					
OTHER COMMENTS					
Investigator Signature:		Data Manager Signature:

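### Grade 5 is barred in Sections 7.2.1–7.2.2 but required on the monitoring form, and Section 11.4.1 neither brings deaths into the toxicity table nor names a safety population

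*Combined protocol and SAP*

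**What the plan says.** **Grading.** Section 7.2.1 lists what is to be evaluated for each AE. The first item is "The severity grade (CTCAE grade 1-4"; the others are relationship, duration and action taken. Section 7.2.2 adds that "CTCAE Grade 5 (death) will not be used in this study" and sends death information to the end-of-treatment or survival page of the CRF.

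**Endpoint.** Section 11.2.1 makes toxicity the second primary endpoint, refers to Section 7 for its definition, and adds: "Adverse events of all grades will be captured by the National Cancer Institute".

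**Monitoring.** The form in Appendix F instructs staff: "RECORD ALL GRADE 3, 4, AND 5 ADVERSE EVENTS (AE". Its key gives 5 as death. Under Section 10.2 the form supports monthly committee review.

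**Analysis.** Section 11.4.1 says: "Adverse events will be tabulated by incidence and severity graded according to the National Cancer Institute". It adds point and two-sided interval estimates of overall and specific toxicity. It gives no death summary, analysis set or confidence level for toxicity.

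**Analysis sets.** Section 11.3.4 names the PSA50 rate, safety and tolerability in one goal. It then puts the initial focus on EEC patients: eligible, on treatment for at least 28 days, and taking at least 75% of Cycle 1 pills. The same section later describes the EEC analysis as an efficacy analysis and treats analyses of non-EEC patients as sensitivity analyses.

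**The concern.** Two instructions to staff cannot both be followed. A fatal AE may not be graded 5 under Sections 7.2.1 and 7.2.2, but the Appendix F form asks for Grade 5 events. The monitoring reports and the final toxicity table could then describe the same event differently.

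Collecting deaths on a separate page is a legitimate convention if the analysis brings them back. Section 11.4.1 does not. A reader of the severity table for a primary endpoint could not tell which events were fatal.

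The second issue is the denominator. If EEC were used for safety, patients who leave before day 28, including those who leave because of toxicity, would drop out of the lead toxicity estimate.

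**Working it through.** **1. Follow one fatal AE through the plan.**
- Section 7.2.1 puts serious events after the start of treatment on the AE form of the CRF, with severity limited to 1–4.
- Section 7.2.2 bars Grade 5. The death goes to another page.
- Section 11.4.1 tabulates by incidence and severity. The event counts in incidence, but its severity column can be Grade 4 at most.
- The four items in Section 7.2.1 do not include outcome. The CRF is not in the documents, so it may hold more, but no planned analysis uses it.
- Section 7.1.6 makes progression that leads to death on study or within 30 days of the last dose a serious event. Progression deaths can therefore enter the same table, unseparated from toxic deaths.
- Section 8.3.5 does have a category "death attributed to drug toxicity", but only within the rule that "Subjects who do not have tumor response assessment due to rapid progression or toxicity will be considered nonresponders". It classifies non-response and is not a safety summary.

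**2. Reproduce the plan's enrolment figure.** Inputs from Section 11.3.4: 27 EEC patients, attrition up to 15%.
- 27 / (1 − 0.15) = 31.8, rounded up to 32. This matches the plan.
- Patients outside EEC: 0.15 × 32 = 4.8, so up to 5 (32 − 27 = 5).

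**3. Illustrate the denominator.** Assumptions: all 32 enrolled patients are treated, exactly one fatal AE occurs, and exact (Clopper–Pearson) 95% intervals are used. The 95% level is assumed because Section 11.4.1 gives none.

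| Where the fatal AE falls | All treated | EEC |
|---|---|---|
| Patient who leaves before day 28 | 1/32 = 3.1% (0.1% to 16.2%) | 0/27 = 0% (0% to 12.8%) |
| EEC patient | 1/32 = 3.1% (0.1% to 16.2%) | 1/27 = 3.7% (0.1% to 19.0%) |

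In the first row the event is absent from the EEC table altogether. In the second row EEC gives a slightly higher rate. The direction of any distortion depends on who leaves and why. Wherever the event does appear, its grade is 4 or lower.

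**4. Could a fatal AE plausibly occur?** The documents give no fatal-AE rate, so a range is assumed. P(at least one in 32) = 1 − (1 − p)^32:
- p = 1%: 27.5%
- p = 2%: 47.6%
- p = 5%: 80.6%

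These figures show only that the case is realistic enough to plan for.

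**The case against.** **Deaths are not lost.** A reader might infer from the bar on Grade 5 that they are. The documents do not support that. Death is a seriousness criterion (Section 7.1.5), and serious events are reported "Within 24 hours of awareness of a serious adverse event, whether or not related to the study drug" (Section 7.4), with seriousness and causality stated. Date of death is collected in survival follow-up (Section 4.2). Deaths within 30 days of the last study intervention and not due to progression go to the IRB (Section 7.3.2). Unexpected, possibly related fatal events go to the FDA within 7 days (Section 7.4.2). This part of the objection stands. What it does not supply is a planned analysis that uses these data.

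**The all-grades wording.** A reader might see a flat contradiction between Section 11.2.1 and Section 7.2.2. But Section 11.2.1 defers to Section 7 for the toxicity definition, so the phrase can mean all grades the study uses. The firm conflict is Sections 7.2.1 and 7.2.2 against Appendix F.

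**The form looks generic.** Its protocol fields are blank and it has a block for dose-escalation trials. It may well be an institutional template that offers one more route for recording fatal AEs. It is nevertheless the form that Section 10.2.3 tells this study to use, and its instruction conflicts with Section 7.2.2.

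**The safety population.** A reader might infer that the plan analyses safety in EEC patients only. The documents do not establish this. Section 11.4.1 does not restrict the AE table, Section 7.1.1 follows AEs from treatment administration without reference to EEC, and Section 11.3.4 keeps non-EEC patients in supplementary analyses. All treated patients is a natural reading. The ambiguity remains because safety and tolerability appear in the sentence that leads into the EEC focus, and no all-treated set is defined.

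**Conclusion.** The point holds in a limited form. Sections 7.2.1 and 7.2.2 conflict with Appendix F on Grade 5. Because Section 11.4.1 has no death summary, the severity table for the second primary endpoint would not distinguish a fatal AE from a survived one. That follows from the text and needs no numerical assumption.

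The missing safety population is an ambiguity. Its possible effect is small in absolute terms: up to 5 of 32 patients could fall outside the lead estimate, and one early fatal AE would read 3.1% or not appear at all. Those figures rest on the plan's own 15% attrition ceiling, all enrolled patients being treated, and a single hypothetical event.

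The safety analysis is descriptive, so no decision rule or sample size depends on this. It should be corrected, with modest priority.

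**What to change.** 1. Reconcile Sections 7.2.1 and 7.2.2 with Appendix F. Either grade fatal AEs 5, or keep the 1–4 scale and add a fatal-outcome row to the Section 11.4.1 tables, linked to the page where death is recorded. Align the form with whichever is chosen.
2. In Section 11.4.1, summarise deaths on study or within 30 days of the last dose as disease progression, drug toxicity or other cause. The list in Section 8.3.5 cannot be reused unchanged: only two of its four categories are deaths, and neither covers another cause.
3. State in Section 11.4.1 that safety analyses include every patient who received at least one dose, and keep EEC for PSA50.

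The cost is protocol wording plus one grade option or one table row. No additional patients are needed, and deaths are already collected. Reported toxicity may look slightly less favourable.

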7.2.3 Attributing causality

After assigning a grade to an adverse event, the investigator must evaluate all AEs for possible causal relationship to the investigational agent. Causality attribution will be decided using the criteria outlined in Table .

Table 8. Relationship of Adverse Event to Study Drug

Relationship	Description
Unrelated	AE is clearly not related
Unlikely	AE is doubtfully related
Possible	AE may be related
Probable	AE is likely related
Definite	AE is clearly related

7.3 Adverse Events Reporting

7.3.1 Regulatory and reporting requirements

These will be followed per IND requirements (if applicable) as well as sponsor requirements and WSU IRB requirements.

7.3.2 WSU IRB Adverse Event Reporting Guidelines

Unexpected Problem – Risk to participant or others. A problem that is a) unforeseen, b) indicates that participants or others are at increased risk of harm, and c) is related or possibly related to the research. The following are examples of unexpected problems:

1. **Adverse Event:** Any harm experienced by a participant regardless of whether the event was internal (on-site) or external (off-site) and regardless of whether the event meets the FDA definition of “serious adverse event”, which in the opinion of the principal investigator are both **unexpected, related (definitely, probably, or more likely than not), and suggests that participants are at greater risk than was previously known or recognized.**
 - a. An adverse event is “unexpected” when its specificity and severity are not accurately reflected in the informed consent document, the protocol or the investigator’s brochure.
 - b. An adverse event is “related to the research procedures” if in the opinion of the principal investigator it was more likely than not to be caused by the research procedures, or if it is more likely than not that the event affects the rights and welfare of current participants.
2. **Any harm experienced by a participant or others** as a result of involvement in research activities (internal or external **excluding** adverse events).
3. Information that indicates a **change to the risks or potential benefits** of the research. For example:
 - a. An interim analysis or safety monitoring report indicates that frequency or magnitude of harm or benefit may be different than initially presented to the IRB.
 - b. A paper is published from another study that shows the risks or potential benefits to your research may be different than initially presented to the IRB.
 - c. Study put on hold by the PI, FDA, or the Sponsor for reasons that may include safety, toxicity and/or efficacy.
4. **A change in FDA labeling** or withdrawal from marketing of a drug, device, or biologic used in a research protocol.
5. **Change to the protocol** taken without prior IRB review to eliminate an apparent immediate hazard to a research participant.
6. **Research conducted without prior WSU IRB approval.**
7. **Event that requires prompt reporting to the sponsor.**
8. **Unanticipated adverse device effect:** Any serious adverse effect on health or safety, or any life-threatening problem or death caused by, or associated with, a device if that effect, problem, or death was not previously identified in nature, severity, or degree of incidence in the investigational plan or application (including a supplementary plan or application), or any other unanticipated serious problem associated with a device that relates to the rights, safety, or welfare of subjects.
9. **Sponsor-imposed suspension for risk.**
10. **Complaint of a participant** when the complaint indicates unexpected risks or cannot be resolved by the research team.
11. **A breach of confidentiality.**

12. **Protocol violation/deviation** (meaning an accidental or unintentional change to the IRB-approved protocol) that harmed participants or others, that indicates participants or others may have been placed at increased risk of harm, or rights of research participants were violated. For example:
 - a. Failure to draw safety labs
 - b. Request for continuation submitted late to the IRB three years in a row
 - c. Wrong informed consent signed or failure to obtain informed consent
13. **Incarceration of a participant** in a protocol not approved to enroll prisoners.
14. **All deaths that have happened at WSU or one of its affiliates within 30 days of the last study intervention, and not related to progressive disease.**
15. **Any death, if the PI feels that it is significant** no matter when it occurs.

IRB Policy

Principal investigators must report any of the above to the IRB as soon as possible, **but in all cases within 5 working days.**

